#### 6.4.2.6. Performance Status

The Karnofsky performance status scores and the change from baseline scores to each subsequent assessment will be summarized. The best and worst changes from baseline during the study will also be summarized. The best change from baseline is defined as the highest change score at post baseline. The worst change from baseline is defined as the lowest change score at post baseline.

## 7. SAFETY ANALYSES

### 7.1. Adverse Events and Deaths

The start of the AE reporting for a study subject will coincide with signing of the informed consent. The end of the adverse-event-reporting period occurs 30 days after discontinuation from study or when any ongoing drug-related AEs and/or serious adverse events (SAEs) have resolved or become stable.

The focus of AE summarization will be on treatment-emergent AEs using the ITT analysis set. All AEs will be listed.

#### 7.1.1. Adverse Event Dictionary

AEs will be coded using the Medical Dictionary for Regulatory Activities (MedDRA) version 15.1. System organ class (SOC), high level group term (HLGT), high level term (HLT), preferred term (PT), and lower level term (LLT) will be attached to the clinical database.

#### 7.1.2. Adverse Event Severity

The severity of AEs will be graded by the investigator according to the CTCAE, Version 3.0, whenever possible. If a CTCAE criterion does not exist, the grade corresponding to the appropriate adjective will be used by the investigator to describe the maximum intensity of the AE. The severity grade will be categorized as:

- Grade 1 (mild)
- Grade 2 (moderate)
- Grade 3 (severe)
- Grade 4 (life threatening), or
- Grade 5 (fatal)

A missing severity grade will be considered as missing.

#### 7.1.3. Relationship of Adverse Events to Study Drug

The investigator-described relationship of the adverse event to the study drug will be categorized as:

- Definite
- Probable

- Possible
- Unlikely, or
- Unrelated

AE will be considered as treatment-related if the causal relationship with study drug is recorded as definite, probable or possible. Events for which the investigator did not record relationship to study drug will be considered related and data listings will show relationship as missing.

#### **7.1.4.                    Serious Adverse Events**

SAEs are those identified as serious in the clinical database. The clinical database will be reconciled with the SAE database from the Drug Safety and Public Health (DSPH) department before database finalization.

#### **7.1.5.                    Treatment-Emergent Adverse Events**

##### **7.1.5.1.                Definition of Treatment-Emergent**

Treatment-emergent AEs are events in a given study period that meet one of the following criteria:

- Events with onset dates on or after the start of treatment and up to 30 days after the permanent discontinuation of the study medication.
- The continuing AEs diagnosed prior to the start of treatment and worsening in severity grade, or non-serious AEs at baseline which become serious, or AEs resulting in treatment discontinuation after the start of treatment.

##### **7.1.5.2.                Incomplete Dates**

All AEs with partial onset or stop dates will be identified and the partial dates will be imputed as follows:

- For AE onset date: If day and month are missing but year is available, then the imputed day and month will be 01Jan or the first dosing date if they have the same year, whichever is later. If day is missing but the month and year are available, then the imputed day will be the first day of the month or the first dosing date if they have the same month and year, whichever is later.
- For AE stop date: If day and month are missing but year is available, then the imputed day and month will be 31Dec or 30 days after the last dose of IDELA if they have the same year, whichever is earlier. If day is missing but the month and year are available, then the imputed day will be the last day of the month or 30 days after the last dose of IDELA if they have the same month and year, whichever is earlier.

### **7.1.6. Summaries of Adverse Events and Deaths**

A brief summary of treatment-emergent AEs will show the number and percentage of subjects who (1) had any AE, (2) had any Grade  $\geq 3$  AE, (3) had any treatment-related AE, (4) had any Grade  $\geq 3$  treatment-related AE, (5) had any SAE, (6) had any treatment-related SAE, (7) discontinued from study drug due to an AE, (8) dose reduction due to an AE, (9) death due to AEs (10) death during study drug treatment up to 30 days post last dose and (11) all deaths including long-term follow up .

Summaries (number and percentage of subjects) of treatment-emergent AEs (by SOC, HLT and PT) will be provided as follows:

- All AEs
- All AEs by severity
- Grade  $\geq 3$  AE
- All AEs occurring in at least 10% of subjects
- All treatment-related AEs
- All treatment-related AEs by severity
- Grade  $\geq 3$  treatment-related AEs
- All SAEs
- All treatment-related SAEs
- All AEs that caused discontinuation from study drug
- AEs leading to deaths

Multiple events will be counted once only per subject in each summary. For data presentation, SOC, HLT and PT will be sorted by decreasing frequency. For summaries by severity grade, the most severe event will be selected. In addition to the presentation by SOC and HLT, each summary listed above will also be presented by preferred term in decreasing frequency.

Summary of all treatment-emergent AEs will also be summarized by SOC, HLT and PT, and by PT only in the following subgroups: sex (Male or Female), age group ( $<65$  or  $\geq 65$  years) and race (White or Non-White).

In addition to the by-treatment summaries, data listings will be provided for the following:

- All AEs (with a variable indicating whether the event is treatment-emergent)

- SAEs (with a variable indicating whether the event is treatment-emergent)
- AEs leading to deaths
- AEs leading to discontinuation of study drug

Relative day from first dose date will be provided for each AE in the listings. If the AE onset date is after the first dose date, the relative day will be calculated as (AE onset date – first dose date + 1), however, if the AE onset date is prior to the first dose date, the relative day will be calculated as (AE onset date- first dose date).

## **7.2. Laboratory Evaluations**

All laboratory data will be listed. Summaries of laboratory data will be based on observed data and will be reported using SI units. The focus of laboratory data summarization will be on treatment-emergent laboratory abnormalities using the ITT analysis set.

### **7.2.1. Summaries of Numeric Laboratory Results**

Descriptive statistics (sample size, mean, standard deviation, median, Q1, Q3, minimum and maximum) will be provided for each laboratory test specified in the study protocol as follows:

- Baseline values
- Values at each post-baseline analysis window
- Change from baseline at each post-baseline analysis window

In the case of multiple values in an analysis window, data will be selected for analysis as described in Section 3.8.3. In addition, the mean change from baseline for lab parameters will be plotted over time.

### **7.2.2. Summaries of Categorical Laboratory Results**

Laboratory data that are categorical will be summarized using number and percentage of subjects in the study with the given response at baseline and each scheduled post-dose assessment.

### **7.2.3. Graded Laboratory Values**

Applicable hematological and serum biochemistry laboratory data will be programmatically graded according to CTCAE, Version 4.03 severity grade [grade laboratory results as Grade 0, mild (Grade 1), moderate (Grade 2), severe (Grade 3), or life threatening (Grade 4)]. Grade 0 includes all values that do not meet criteria for an abnormality of at least Grade 1. Some laboratory tests have criteria for both increased and decreased levels; analyses for each direction (ie, increased, decreased) will be presented separately.

#### **7.2.3.1. Treatment-Emergent Laboratory Abnormalities**

A treatment-emergent laboratory abnormality is defined as an abnormality that, compared to baseline, worsens by  $\geq 1$  grade in the period from the first dose of IDELA to 30 days after the last dose of study treatment. If baseline data are missing, then any graded abnormality (ie, an abnormality that is Grade  $\geq 1$  in severity) will be considered treatment-emergent.

#### **7.2.3.2. Summaries of Laboratory Abnormalities**

The following summaries (number and percentage of subjects) of treatment-emergent laboratory abnormalities will be provided (subjects will be categorized according to most severe abnormality grade):

- Baseline and worst post-baseline laboratory abnormalities
- Grade  $\geq 3$  laboratory abnormalities

For all summaries of laboratory abnormalities, the denominator is the number of subjects in the ITT analysis set. A listing of treatment-emergent Grade  $\geq 3$  laboratory abnormalities will be provided.

### **7.2.4. Shift in CTCAE Grade Relative to Baseline**

Shift tables will be presented by showing change in CTCAE severity grade from baseline to the worst grade post baseline.

### **7.2.5. Transaminase elevations**

Analysis of transaminase elevations will be based on laboratory values. Number and percentage of subjects will be summarized for subjects

- with Grade 3 or 4 ALT/AST elevation
- with Grade 3 or 4 ALT/AST elevation resolved to both ALT/AST of Grade 1 or less
- re-challenged after dose interruption due to Grade 3 or 4 ALT/AST elevation

- with recurrence of grade 3 or 4 ALT/AST elevation
- with recurrent Grade 3 or 4 ALT/AST elevation resolved to both ALT/AST of Grade 1 or less

Kaplan-Meier curves and estimates will be provided for time to onset of first Grade 3 or 4 treatment-emergent ALT/AST elevations. Time to onset of first event is defined as time from start of study treatment to the start date of first Grade 3 or 4 treatment-emergent ALT/AST elevation, ie, time in days is calculated as (start date of first occurrence) – (date of first dose of study drug) +1. In the absence of an event, the censoring date applied will be the earliest from the following dates: last dose date (if treatment discontinued) + 30 days, analysis data cut-off date and death.

For subjects with at least 1 episode of Grade 3 or 4 ALT/AST elevation, time to resolution of first episode of treatment-emergent Grade 3 or 4 ALT/AST elevation to Grade 1 or less will be summarized using Kaplan-Meier estimates. The same censoring rule described above for time to onset will be used. In addition, the same analysis will be performed for subjects who are rechallenged due to Grade 3 or 4 treatment-emergent ALT/AST elevations.

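### Time to resolution of Grade 3/4 ALT/AST elevation borrows the onset censoring rule (last dose + 30 days, data cut-off or death), which does not suit recovery and can bias the estimate in either direction

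*SAP*

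**What the plan says.** Section 7.2.5 plans two Kaplan-Meier analyses of transaminase elevation, reported together in Table 3.2.2.5.

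- **Onset.** Time runs from first dose to the first treatment-emergent Grade 3 or 4 ALT/AST elevation. Censoring uses whichever of three dates comes first, namely "last dose date (if treatment discontinued) + 30 days, analysis data cut-off date and death". It applies only to subjects with no recorded event.
- **Resolution.** For subjects with at least one such episode, "time to resolution of first episode of treatment-emergent Grade 3 or 4 ALT/AST elevation to Grade 1 or less will be summarized using Kaplan-Meier estimates". On censoring: "The same censoring rule described above for time to onset will be used". The analysis is repeated for rechallenged subjects.

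Three other statements bear on this:

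- Section 7.2.3.1 calls a laboratory abnormality treatment-emergent if it worsens "in the period from the first dose of IDELA to 30 days after the last dose of study treatment".
- Section 7.2.5 also counts subjects "with Grade 3 or 4 ALT/AST elevation resolved to both ALT/AST of Grade 1 or less", with no time limit stated.
- Section 7.1 lets adverse event reporting end 30 days after discontinuation from study, or "when any ongoing drug-related AEs and/or serious adverse events (SAEs) have resolved or become stable".

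**The concern.** A limit of 30 days after last dose is natural for onset, because that is where the treatment-emergent window closes. Recovery has no such window. An elevation that begins on day 30 after last dose is treatment-emergent under Section 7.2.3.1, yet if unresolved it is censored with no follow-up at all.

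The rule also departs from the SAP's own practice. Subjects without an event are censored at the last tumor assessment for DOR and PFS (6.4.2.1), at the last available PRO assessment for symptom response (6.4.2.5) and when last known alive for OS (6.4.2.4). None of the three dates used for resolution is the last ALT/AST value.

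At stake is how quickly, and how completely, a liver signal with its own safety section is reported to reverse, particularly in subjects who permanently stopped drug.

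**Working it through.** The SAP gives no figure for time to resolution, so there is none to reproduce. Recovery times and the share who stop drug are not in the document either; every value below marked as assumed is mine. Recovery is taken as exponential.

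**1. What the borrowed rule does with a late resolution.** The rule applies only where there is no event, so two readings are open for a subject who stopped drug and resolved after last dose + 30 days.

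- *Cut:* follow-up ends at +30 days and the later resolution is not counted.
- *Keep:* the resolution counts as an event when it occurs, and only subjects who never resolve are censored, at +30 days.

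**2. Size under the cut reading, closed form.** Assumed: share p = 0.40 stop at onset; median recovery 8 weeks in stoppers and 3 weeks in the rest; cut at c = 30/7 = 4.286 weeks.

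- Full follow-up: S(t) = p·2^(−t/8) + (1−p)·2^(−t/3).
- Cut: the same up to c; after c only non-stoppers are at risk, so S_cut(t) = S(c)·2^(−(t−c)/3).
- Stoppers censored unresolved: 2^(−4.286/8) = 0.69.
- S(c) = 0.40 × 0.690 + 0.60 × 0.3715 = 0.499.
- Unresolved at 12 weeks, full: 0.40 × 0.3536 + 0.60 × 0.0625 = 0.179.
- Unresolved at 12 weeks, cut: 0.499 × 2^(−7.714/3) = 0.499 × 0.168 = 0.084.
- 75th percentile of recovery time: about 9.3 weeks full, 7.3 weeks cut.
- Median: 4.27 weeks both ways, because half have resolved just before c.

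With p = 0.30, unresolved at 12 weeks is 15.0% full and 7.9% cut; the median is 3.88 weeks both ways.

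**3. Direction under both readings, simulation.** Assumed: 200,000 subjects; 60% stop, with last dose 0 to 7 days after onset; median recovery 28 days in those who continue; late results available to last dose + 90 days. Cumulative proportion resolved at day 60 / day 90:

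| Stoppers' median | Episodes censored unresolved under cut | Full follow-up | Cut | Keep |
|---|---|---|---|---|
| 28 days (equal) | 26% | 0.772 / 0.892 | 0.773 / 0.891 | 0.805 / 0.943 |
| 56 days (slower) | 40% | 0.623 / 0.759 | 0.700 / 0.856 | 0.718 / 0.923 |
| 14 days (faster) | 12% | 0.879 / 0.951 | 0.851 / 0.930 | 0.883 / 0.956 |

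Under *cut*, there is no bias at equal rates, recovery looks faster if stoppers are slower, and slower if stoppers are faster. In the middle row the median does move: 42.0 days full, 39.4 cut. If every affected subject stops, the cut curve ends 30 to 37 days after onset.

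Under *keep*, resolution is overstated in all three rows; at day 90 the excess runs from 0.956 − 0.951 = 0.005 to 0.923 − 0.759 = 0.164. The mechanism needs no difference in recovery rates: after +30 days the only stoppers still at risk are those who go on to resolve.

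**4. Subjects still on drug.** They have no last dose + 30 days date, so an unresolved subject is censored at data cut-off (or death). The time between the last ALT/AST value and cut-off is then counted as observed and unresolved, which makes recovery look slower. On scheduled visits alone that gap can reach about 12 weeks after Week 48 (Section 1.2).

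**The case against.** A reader might infer that the plan discards late recoveries and thereby makes recovery look faster. The SAP does not support that.

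- Discarding is only one reading. Because the rule applies in the absence of an event, late resolutions may be kept.
- Under the cut reading, faster needs stoppers to recover more slowly. The SAP has no data on this, and the direction reverses if they recover faster.
- Censoring at data cut-off for subjects still on drug works the other way, so no net direction can be claimed.

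Other points on that side also stand. Stoppers' resolutions count up to last dose + 30 days on either reading, and only permanent discontinuation triggers the limit, so subjects who merely interrupt dosing are unaffected. Stopping long after an episode has resolved loses nothing. The companion count of resolved subjects and the laboratory listings (7.2) would still show non-resolvers.

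Section 7.1 is weak evidence that later laboratory data exist: it governs adverse event reporting, whereas "Analysis of transaminase elevations will be based on laboratory values". As far as the Section 1.2 schedule can be read, serum chemistry is marked through Visit 16+ and not in the follow-up columns. How many ALT/AST values lie beyond 30 days cannot be established from the SAP; if there are few, the cut loses little.

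These arguments limit the size and remove a fixed direction. They do not rescue the rule, since neither reading gives a sound estimate and none of the three dates is tied to the last ALT/AST value.

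**Conclusion.** The point holds as a defect in a stated rule. A censoring rule built for treatment-emergent onset is applied unchanged to recovery. If follow-up is cut at +30 days, the estimate loses later resolutions and is biased either way when stoppers recover at a different rate; at equal rates it loses only precision. If late resolutions are kept, censoring depends on the outcome and resolution is overstated. Separately, unobserved time in subjects still on drug counts as unresolved.

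The size rests on assumed inputs. The 8% against 18% unresolved at 12 weeks belongs to 40% stopping at onset with medians of 8 and 3 weeks. The unchanged median of about 4.3 weeks in that case depends on half having resolved before the 30-day cut and is not general. This is a minor point: the analysis is a descriptive safety summary and does not touch the primary endpoint or power.

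**What to change.** In Section 7.2.5, replace the sentence that carries the onset rule over to resolution. For time to resolution, count a resolution whenever it is observed up to data cut-off, and censor unresolved subjects at their last ALT/AST assessment on or before data cut-off, with no last dose + 30 days limit. Keep the 30-day rule for time to onset only. Apply the same resolution rule to the rechallenge analysis. The same edit could state the time origin for resolution and how deaths before resolution are handled.

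The cost is one SAP sentence and a separate derived censoring variable for Table 3.2.2.5. No data collection or clinical rule changes. If few ALT/AST values exist beyond 30 days after last dose, the result for subjects who stopped will change little and the change does no harm.

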### **7.3. Vital Signs**

Vital sign data (body temperature, sitting systolic and diastolic blood pressures, and sitting pulse rate) will be summarized in the following tables:

- Actual values and the changes from baseline by visit for each measure
- Number and percent of subjects by systolic (SBP) and diastolic blood pressure (DBP) category (high, normal, low) at each visit categorizing SBP  $\geq$  140 mmHg as high and  $<$  90 mmHg as low; DBP  $\geq$  90 mmHg as high and  $<$  60 mmHg as low.

Data for body weight and height will be listed with the vital signs as collected in the CRF. High or low values for vital signs will be flagged.

### **7.4. Prior Therapy and Prior Radiation**

Number of prior regimens and time since the completion of last regimen will be summarized using descriptive statistics (sample size, mean, standard deviation, median, Q1, Q3, minimum and maximum). A partial completion date will be imputed using the following algorithm for the last regimen:

- If day and month are missing but year is available, then the imputed day and month will be 01Jan or the starting date of the last regimen, whichever is later;
- If day is missing but the month and year are available, then the imputed day will be the first day of the month, or the starting date of the last regimen, whichever is later;

- If year is missing, no imputation will be done and the completion date will be treated as missing.

Number (%) of subjects who received 1, 2, 3, ... prior regimens will also be provided. In addition, number (%) of subjects refractory to rituximab, refractory to alkylating-agent, refractory to bendamustine, and refractory to last therapy will also be summarized.

Descriptive statistics will be provided for number of subjects who received certain regimens (eg, BR, CHOP, R-CHOP). Descriptive statistics will also be provided for the last regimen subjects received prior to study entry. The best response (n, %) to last therapy, and duration of response to the last therapy will be summarized.

Number of subjects received prior radiation will be summarized and will be listed.

## **7.5. Concomitant Medications**

Concomitant medications will be coded by means of the World Health Organization Drug Dictionary (WHO DRUG) dictionary, June 2010 into Anatomical-Therapeutic-Chemical classification (ATC) codes.

Concomitant medications are defined as any medications meeting the following criteria:

- Starting on or after the first dose of IDELA treatment up to 30 days post the last dose
- Starting before and continuing after the first dose of IDELA treatment up to 30 days post the last dose

The incomplete dates handling method used for AE summaries will be used for concomitant medication summaries (section 7.1.5.2).

Prior medications are defined as any medications stopped before the first dose of study drug. Summaries of the number and percentage of subjects who used prior and concomitant medications will be presented in tabular form by preferred drug name based on ITT analysis set. The summary tables will be sorted by descending frequency of preferred term in the total column. Subjects will only be counted once for multiple drug use (by preferred drug name) per subject.

Concomitant medications started on/-after the start of study medication or ongoing medications will be flagged on the prior and concomitant medication data listing.

The summaries and listings will be based on the ITT analysis set.

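### A partial start date that shares its month or year with the first dose is moved to the first dose without checking for an earlier known stop date

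*SAP*

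**What the plan says.** SAP Section 7.1.5.2 gives the rule for partial adverse event onset dates. With day and month missing, "the imputed day and month will be 01Jan or the first dosing date if they have the same year, whichever is later". With only the day missing, "the imputed day will be the first day of the month or the first dosing date if they have the same month and year", again taking the later of the two. The same section has a separate rule for partial stop dates, but the onset rule makes no reference to the stop date.

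Section 7.5 carries the method over to medications, with no exception: "The incomplete dates handling method used for AE summaries will be used for concomitant medication summaries (section 7.1.5.2".

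Three definitions then use these dates:

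- Treatment-emergent, first criterion (Section 7.1.5.1): "Events with onset dates on or after the start of treatment and up to 30 days after the permanent discontinuation" of study medication.
- Concomitant, first criterion (Section 7.5): "Starting on or after the first dose of IDELA treatment up to 30 days post the last dose".
- Prior (Section 7.5): "Prior medications are defined as any medications stopped before the first dose of study drug".

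The first two look only at the start date and the third only at the stop date. Adverse events that end before dosing can be in the database, because Section 7.1 states: "The start of the AE reporting for a study subject will coincide with signing of the informed consent". Section 1.2 allows a screening period of up to 4 weeks.

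**The concern.** Moving an uncertain onset to the first dose is a familiar cautious convention. It is defensible while nobody knows whether the event or drug overlapped treatment. A recorded stop date before the first dose removes that doubt. The rule then overrides recorded data and yields an impossible record whose start falls after its stop.

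Because the definitions of treatment-emergent and concomitant have a criterion that rests on the start date alone, the impossible start is enough to change the classification. This is a single-arm study with no control group in which the same artefact would also appear. An event that resolved in screening would be reported in the treatment-emergent tables (the 3.1 series) as part of the experience on idelalisib. A drug already stopped would qualify for the concomitant medication table (Table 1.7).

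**Working it through.** The plan gives no figure to reproduce here, so the check applies the rule as written to test records.

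**Inputs.** The onset rule is from Section 7.1.5.2 and the classification rules are from Sections 7.1.5.1 and 7.5. The dates are illustrative: first dose F = 20 March 2012, last dose 1 December 2012.

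**Rule as written**, with S the imputed start:

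- Day missing: S = max(first of month, F) if month and year match F; otherwise S = first of month.
- Day and month missing: S = max(1 January, F) if the year matches F; otherwise S = 1 January of the recorded year.

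**Classification.** The start-date criterion (treatment-emergent or concomitant) is met if F ≤ S ≤ last dose + 30 days. A drug is prior if stop < F.

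| Case | Recorded start | Known stop | Imputed start S | S after stop | Start-date criterion | Prior |
|---|---|---|---|---|---|---|
| a | March 2012 | 10 Mar 2012 | max(1 Mar, 20 Mar) = 20 Mar 2012 | yes, by 10 days | met | met |
| b | 2012 | 5 Feb 2012 | max(1 Jan, 20 Mar) = 20 Mar 2012 | yes, by 44 days | met | met |
| c | February 2012 | 10 Mar 2012 | 1 Feb 2012 | no | not met | met |
| d | 2011 | 10 Mar 2012 | 1 Jan 2011 | no | not met | met |

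Cases a and b fail; c and d do not. The error needs three things together: a partial start, a match with the month and year (or year) of the first dose, and a stop known to precede the first dose. As adverse events, a and b could not qualify under the second treatment-emergent criterion, which concerns events continuing into treatment. Only the imputed onset makes them treatment-emergent.

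**With a cap**, S′ = min(S, stop) whenever stop < F:

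- Case a: min(20 Mar, 10 Mar) = 10 Mar 2012.
- Case b: min(20 Mar, 5 Feb) = 5 Feb 2012.

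Both now start before F and neither starts after its stop. Both are prior only as drugs and not treatment-emergent as events.

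**How often the date match alone occurs for screening events.** The SAP gives no rate, so this rests on assumptions: onset uniform over the 28 days before first dose, and first dose uniform over the 366 days of 2012. That gives 366 × 28 = 10,248 equally likely pairs.

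- Same month and year as the first dose: a 31-day month contributes 462 pairs, a 30-day month 434 and the 29-day February 406. The total is 7 × 462 + 4 × 434 + 406 = 5,376, and 5,376 / 10,248 = 52%.
- Same year: only first doses on 1 to 28 January can have an onset in the previous year, which is 28 + 27 + … + 1 = 406 pairs. So 1 − 406 / 10,248 = 96%.

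These are the shares of screening onsets that the rule would move if the day (52%) or the day and month (96%) were missing. They are not shares of misclassified events, because a partial onset and a known pre-dose stop are also needed.

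**The case against.** The strongest reply is that this is narrow and errs on the safe side. An affected adverse event must begin and end within at most 4 weeks of screening, with its stop known, its onset day unknown, and a matching month or year. The outputs are descriptive, and counting too many treatment-emergent events does not flatter the drug. All of that stands as to size. It does not justify the rule, since a known earlier stop leaves nothing to be cautious about.

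Several stronger readings are tempting, and the SAP does not support them:

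- *Every incomplete start is moved to the first dose.* It is not; cases c and d show that the period must match.
- *Affected drugs are counted twice.* They meet both definitions, but the SAP does not say which prevails. Because the stop date is complete, one could fairly class such a drug as prior before imputing anything. The appendix lists a concomitant table (1.7) and no separate prior-medication table. The overlap is real, but a double count in the output is only one possible consequence.
- *Long-standing drugs will be reported as new starts on Day 1.* A drug still in use at first dose is concomitant under either criterion, and Section 7.5 flags new and ongoing drugs together. No planned table counts new starts, and the SAP does not say that listings show imputed dates.
- *A number of misclassified records can be given.* No rate of partial dates is stated. The tables also count subjects, once per drug name or event term, so a record count would not carry over.

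**Conclusion.** The point holds as a minor defect. The onset rule in Section 7.1.5.2, and Section 7.5 through its cross-reference, give a wrong classification for records with a matching partial start and a stop known to precede the first dose. Nothing else in the SAP corrects it. An event resolved in screening becomes treatment-emergent, and a stopped drug satisfies the concomitant and prior definitions at once.

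The effect reaches only the treatment-emergent adverse event and concomitant medication summaries. It is probably small, although the SAP offers no data from which to size it. The primary response rate analysis, duration of response, progression-free survival and overall survival do not use this rule. The conclusion assumes that the rule is programmed literally. A programmer might correct the dates on their own initiative, but that would be an undocumented departure from the plan.

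**What to change.** Add to Section 7.1.5.2, applying by reference to Section 7.5: if the stop date, or the latest date that a partial stop date allows, is before the first dose, the imputed start may not be later than that stop date, and the record is classed as pre-treatment (adverse event) or prior only (medication). Keep the existing rule for every other record, including those with a missing stop date.

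The SAP already uses this kind of bound: Section 7.4 does not let an imputed completion date for the last regimen fall before that regimen's start.

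A separate rule for medication starts in Section 7.5 is not needed and could do harm. If partial starts were always set to the beginning of the known period, a drug with no stop date and no ongoing mark could drop out of the concomitant class, because its continuation past the first dose could not be shown.

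The cost is one added rule in the SAP and a small programming change. No new data are needed, and the cautious handling of ambiguous records is unchanged.
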